6.2.2 Statistics for Continuous and Categorical Variables

Continuous variables will be summarized using the following descriptive summary statistics: the number of participants (n), mean, standard deviation (SD), median, minimum (min), and maximum (max).

Categorical variables will be summarized using frequencies and percentages.

6.2.3 Baseline

Baseline results for laboratory measurements, vital signs, immunogenicity, and nasopharyngeal (NP) swab tests will be defined as the last recorded non-missing value prior to study vaccine administration.

6.2.4 Reference Start Date and Study Day

The reference start date is used as the time point from which the study day is calculated. Study days prior to the reference start date will be negative, while study days after the reference start date are positive.

The reference start date is the date of study vaccine administration.

Study day will be calculated as follows:

- Study day prior to vaccination will be calculated as:
date of assessment/event – the reference start date

- Study day on or after the date of vaccination will be calculated as:
date of assessment/event – the reference start date + 1.

An assessment/event date on the reference start date will be study day 1.

6.2.5 Handling Non-Quantifiable Antibody Values

For calculation regarding antibody levels/titers, antibody values reported as below lower limit of quantification (LLOQ) will be replaced by $0.5 \times \text{LLOQ}$. Values that are greater than the upper limit of quantification (ULOQ) will be converted to the ULOQ. Missing results will not be imputed.

6.2.6 Analysis Periods for Safety Analyses

The following analysis periods for safety analyses will be used in this study:

- 7 days following vaccination: this period includes the day of vaccination and 6 subsequent days. This analysis period will be used for solicited local and systemic ARs that occur during this time.
- 28 days following vaccination: this period includes the day of vaccination and 27 subsequent days. This analysis period will be used for unsolicited AEs.
- Overall period: this analysis period starts on Day 1 and continues through the earliest of the following: Day 181/study completion, discontinuation from the study, or death.

6.2.7 Unscheduled Visits and Visit Windowing Rules

Unscheduled visit measurements will be included in analysis as follows:

- In scheduled visit windows per specified visit windowing rules.
- In the derivation of baseline/last on-treatment values.
- In the derivation of max/min on-treatment values and max/min change from baseline values for safety analyses.
- In individual participant data listings as appropriate.

The analysis visit windows for protocol-defined visits are provided in [Appendix B](#).

6.2.8 Handling Missing and Incomplete Data

- Imputation rules for missing dates of prior/concomitant medications, non-study vaccinations and procedures are provided in [Appendix C](#).
- Imputation rules for missing AE dates are provided in [Appendix D](#).
- For laboratory assessments, if majority of results are indefinite, imputation of these values will be considered. If the laboratory results are reported as below the LLOQ (e.g., < 0.1), the numeric values will be replaced by $0.5 \times \text{LLOQ}$ in the summary. If the laboratory results are reported as greater than the ULOQ (e.g., > 3000), the numeric values will be replaced by ULOQ in the summary.
- Other incomplete/missing data will not be imputed, unless otherwise specified.

6.2.9 Age and Vaccination Groups

Age groups:

The following age groups will be used for summary purposes:

- Overall
- Age: ≥ 18 to < 50 years
- Age: ≥ 50 to ≤ 75 years

Vaccination groups:

The following vaccination groups will be used for summary purposes:

- mRNA-1030 CCI
- mRNA-1020 CCI
- mRNA-1030 CCI
- mRNA-1020 CCI
- mRNA-1030 CCI
- mRNA-1020 CCI
- mRNA-1010 50 μg
- Flublok 180 μg

All analyses and data summaries/displays will be provided by vaccination group (and then by age group) using appropriate analysis population, unless otherwise specified.

6.2.10 Adjustment for Covariates

The estimates of GMFR with 95% CIs will be calculated based on analysis of covariance (ANCOVA) model adjusted for baseline titer, age group and /or other covariates. Antibody titers are analyzed using \log_2 titers or \log_2 fold rise and back transformed to estimate GMFRs with 95% CIs. After transformation, the data tend to be normally distributed.

6.3 Background Characteristics

The following description of background characteristics analyses will be applied to this study, unless otherwise specified.

6.3.1 Participant Disposition

The number and percentage of participants in the following categories will be summarized by randomized vaccination group and then further by age group as defined in [Section 6.2.9](#) based on Randomization Set:

- Randomization Set
- Full Analysis Set (FAS)
- Per-protocol (PP) Set
- Safety Set
- Solicited Safety Set

The percentage will be based on participants in that vaccination group within the Randomization Set. A summary of reasons for participants who are in the Randomization Set but excluded from PP Set will also be provided. Listing of analysis sets will be provided based on the Randomization Set.

The number of participants in the following categories will be summarized based on participants screened:

- Number of participants screened
- Number and percentage of screen failure participants and the reason for screen failure

The percentage of participants who screen failed will be based on the number of participants screened. The percentage of participants for each reason for screen failure will be based on the number of participants who screen failed. For screened failure participants, age (years), as well as sex, race, ethnicity, and reasons for screen failure will be presented in a listing.

The number and percentage of participants in each of the following disposition categories will be summarized by vaccination group (and then by age group) based on the Randomization Set:

- Received injection
- Completed study
- Discontinued from the study and the reason for discontinuation

A participant disposition listing will be provided, including informed consent date, injection date, date of study completion, date of study discontinuation, with reasons for discontinuation.

A participant who completed Day 181/EoS (Month 6 visit), defined as 6 months after the study vaccination on Day 1, is considered to have completed the study.

6.3.2 Demographics

Descriptive statistics will be calculated for the following continuous demographic and baseline characteristics: age (years), weight (kg), height (cm), and body mass index (BMI) (kg/m^2). Number and percentage of participants will be provided for categorical variables such as gender, race, and ethnicity. The summaries will be presented by vaccination group and overall based on the Randomization Set, FAS, PP Set, and Safety Set. If the Safety Set differs from the Randomization Set (e.g., participants randomized but not received any study vaccination or participants received study vaccination other than the vaccination group they were randomized to), the analysis will also be conducted using the Randomization Set. Summary of RT-PCR SARS-CoV-2 results at baseline, baseline RT-PCR Influenza Results and Seasonal Influenza Vaccine since Sep 2021.

Listing of demographics and baseline characteristics will be provided based on the Randomization Set.

6.3.3 Medical History

Medical history data will be coded by system organ class (SOC) and preferred term (PT) using the Medical Dictionary for Regulatory Activities (MedDRA).

The number and percentage of participants with any medical history will be summarized by SOC and PT based on the Safety Set. A participant will be counted only once for multiple events within each SOC and PT. SOCs will be displayed in internationally agreed order. PTs will be displayed in descending order of frequency in total of each type of vaccination group/overall group and then alphabetically within SOC.

Medical history data will be presented in a listing.

6.3.4 Prior and Concomitant Medications

Prior and concomitant medications and non-study vaccination will be coded using the World Health Organization drug dictionary (WHODrug Global). The summary of concomitant medications will be based on the Safety Set. Categorization of prior, concomitant, and post medications is summarized in [Appendix C](#).

The number and percentage of participants using concomitant medications and non-study vaccination during the 7-day follow-up period (i.e., on the day of injection and the 6 subsequent days) and during the 28-day follow-up period after the injection (i.e., on the day of injection and the 27 subsequent days) will be summarized by vaccination groups as follows:

- Any concomitant medications and non-study vaccination within 7 days post-injection
- Any concomitant medications within 28 days post-injection
- Any non-study vaccination within the period starting 28 Days before IP Injection and through Day 181/EoS
- Any Seasonal influenza vaccine from September 2021 through Day 181/EoS
- Any Covid-19 Vaccine before the IP Injection and through Day 181/EoS
- Antipyretic or analgesic medication within 28 days post-injection

A summary table of concomitant medications and non-study vaccination that continued or was newly received on the date of injection through 28 days post-injection will be provided by PT in descending frequency in the total group.

Medications taken to prevent or treat pain or fever within 7 days after injection will be collected in the electronic diary (eDiary), and summaries will be provided based on the Solicited Safety Set by vaccination group (and then by age group) as defined in [Section 6.2.9](#).

Prior, concomitant, post medications, and non-study vaccination will be presented in a listing. Medications taken to prevent or treat pain or fever will also be presented in a listing.

Concomitant procedures will be presented in a listing.

6.3.5 Study Exposure

Study IP administration data will be presented in a listing. Participants with dosing error will be presented in a listing.

Study duration will be summarized from randomization and from the injection based on the Safety Set.

6.3.6 Major Protocol Deviations

Major protocol deviations are a subset of protocol deviations that may significantly impact the completeness, accuracy, or reliability of the study data or that may significantly affect a participant's rights, safety, or well-being. Major protocol deviations rules will be developed and finalized before database lock.

The number and percentage of the participants with each major protocol deviation type will be provided by vaccination group (and then by age group) based on the Randomization Set.

Major protocol deviations will be presented in a listing.

If the protocol deviations (PDs) are classified as Important/Non-Important', then Important means Major and Non-Important means Minor.

6.3.7 COVID-19 Impact

A listing will be provided for the impact of coronavirus disease 2019 (COVID-19) on the execution of the study.

6.4 Safety Analysis

All safety analyses will be based on the Safety Set, except summaries of solicited ARs, which will be based on the Solicited Safety Set. All safety analyses will be provided by vaccination group and by age group. Participants will be included in the vaccination group corresponding to what they actually received.

Safety and reactogenicity will be assessed by clinical review of all relevant parameters including the following:

- solicited local and systemic ARs
- unsolicited AEs (including any clinical safety laboratory abnormalities)
- treatment-related AEs
- severe AEs
- SAEs
- AESIs
- MAAEs
- AEs leading to withdrawal from study participation
- vital sign measurements
- physical examination findings

Unsolicited AEs will be coded by system organ class (SOC) and preferred term (PT) according to MedDRA. Solicited ARs will be coded according to the MedDRA for AR terminology.

All table data will have a corresponding listing. Safety phone calls data will be provided in a listing. Deaths will be provided in a listing.

6.4.1 Unsolicited Adverse Events

An unsolicited AE is any AE reported by the participant that is not specified as a solicited AR in the protocol or is specified as a solicited AR but starts outside the protocol-defined period for reporting solicited ARs (i.e., for the 7 days after the injection of IP).

Only treatment-emergent AE (TEAE) will be included in the analysis. A TEAE is defined as any event occurring during the study not before exposure to study vaccine or any event already present that worsens in intensity or frequency after exposure to study vaccine.

AEs will also be evaluated by the investigator for MAAE and AESI. An MAAE is defined as an AE that leads to an unscheduled visit to a healthcare practitioner (HCP). An AESI is an AE (serious or nonserious) of scientific and medical concern specific to the Sponsor's product or program, for which ongoing monitoring and immediate notification by the Investigator to the Sponsor are required. The AESIs for this study are listed in [APPENDIX 3](#) of the protocol Section 11.3.

Unsolicited AEs within 28 days after vaccination will be summarized by vaccination group. Unsolicited SAE, unsolicited AESI, unsolicited MAAE, and unsolicited AE leading to withdrawal from the study up to 28 days after vaccination and overall period will be summarized by vaccination group. See [Section 6.2.9](#) and [Section 6.2.6](#) for definitions of analysis groups and analysis period respectively.

All summary tables (except for the overall summary of AEs) for unsolicited TEAEs will be presented by SOC and/or PT, and by SOC and PT and severity, with counts of participants included. SOCs will be displayed in internationally agreed order. PTs will be displayed in descending order of frequency of total in each vaccine type group and then alphabetically within SOC. When summarizing the number and percentage of participants with an event, participants with multiple occurrences of the same AE or a continuing AE will be counted once. Participants will be presented according to the highest severity in the summaries by severity, if participants reported multiple events under the same SOC and/or PT.

Percentages will be based upon the number of participants in the Safety Set within each vaccination group.

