Arthralgia (joint aches in several joints)	None	No interference with activity	Some interference with activity	Significant; prevents daily activity	Requires emergency room visit or hospitalization				

Page 64 Confidential

Reaction	Grade 0 (None)	Grade 1 (Mild)	Grade 2 (Moderate)	Grade 3 (Severe)	Grade 4 (Life- Threatening)
Nausea/vomiting	None	No interference with activity or 1-2 episodes/ 24 hours	Some interference with activity or > 2 episodes/24 hours	Prevents daily activity, requires outpatient intravenous hydration	Requires emergency room visit or hospitalization for hypotensive shock
Chills	None	No interference with activity	Some interference with activity not requiring medical intervention	Prevents daily activity and requires medical intervention	Requires emergency room visit or hospitalization
Fever (oral)	< 38.0°C < 100.4°F	38.0 – 38.4°C 100.4 – 101.1°F	38.5 – 38.9°C 101.2 – 102.0°F	39.0 – 40.0°C 102.1 – 104.0°F	> 40.0°C > 104.0°F

Note: Events listed above but starting > 7 days post study injection will be recorded on the AE page of the eCRF. Causality for each event will be determined per assessment by the Investigator.

Source: DHHS 2007

Any solicited AR that meets any of the following criteria must be entered into the participant's source document and must also be recorded by the study site staff in the solicited AR section of the participant's eCRF:

- Solicited local or systemic AR that results in a visit to a healthcare practitioner (HCP), to be recorded as an MAAE (Section 8.4.4).
- Solicited local or systemic AR leading to the participant withdrawing from the study or the participant being withdrawn from the study by the Investigator (AE leading to withdrawal).
- Solicited local or systemic AR continuing beyond 7 days post injection.
- Solicited local or systemic AR that otherwise meets the definition of an SAE.

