3 STUDY ENDPOINTS

3.1 Primary Endpoints

Safety

- Frequency and grade of each solicited local and systemic reactogenicity adverse reaction (AR) during a 7-day follow-up period post-vaccination
- Frequency and severity of any unsolicited adverse events (AEs) during the 28-day follow-up period post-vaccination
- Frequency of any serious adverse events (SAEs), adverse events of special interest (AESIs), medically attended adverse events (MAAEs), and AEs leading to withdrawal from Day 1 through Day 181/end of study (EoS)
- Safety laboratory abnormalities through 7 days post-vaccination

Immunogenicity

- Geometric mean titer (GMT) and geometric mean fold rise (GMFR) at Day 29 compared with Day 1 (baseline) and percentage of participants with seroconversion, defined as a Day 29 titer $\geq 1:40$ if baseline is $< 1:10$ or a 4-fold or greater rise if baseline is $\geq 1:10$ in anti-hemagglutinin (HA) antibodies measured by hemagglutination inhibition (HAI) assay
- GMT and GMFR of anti-neuraminidase (NA) measured by neuraminidase inhibition (NAI) assay at Day 1 and Day 29 and percentage of participants with a change in the Day 29 titer of at least 2-/3-/4-fold rise, defined as $\geq 2-/3-/4$ -fold of

the lower limit of quantification (LLOQ) if the Day 1 titer is < LLOQ; or $\geq 2\text{-}3\text{-}4\text{-}$ fold of the Day 1 titer if the Day 1 titer is \geq LLOQ

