6.4.1.1 Incidence of Unsolicited Adverse Events

An overall summary of unsolicited TEAEs including the number and percentage of participants who experience the following within 28 days after vaccination (See [Section 6.2.6](#) for safety analysis periods) will be presented:

- Any unsolicited TEAEs (See [Section 6.2.6](#) for study periods)
- Any unsolicited serious TEAEs
- Any unsolicited fatal TEAEs
- Any unsolicited medically attended TEAEs
- Any unsolicited treatment-emergent AESI

- Any unsolicited TEAEs leading to discontinuation from participation in the study
- Any unsolicited severe TEAEs

The table will also include number and percentage of participants with unsolicited TEAEs within 28 days after vaccination that are treatment-related in each of the above categories.

In addition, separate listings containing individual participant AE data for unsolicited TEAEs, unsolicited TEAEs leading to withdrawal from study participation, unsolicited AESI, and unsolicited medically attended TEAEs will be provided. Unsolicited treatment-related TEAEs, unsolicited severe TEAEs, unsolicited treatment-related severe TEAEs, unsolicited serious treatment-related AEs, unsolicited treatment-related medically attended TEAEs, unsolicited adverse events leading to death, and unsolicited TEAEs for participants with influenza or SARS-CoV-2 infection will also be provided in corresponding listings.

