6.4.1.2 TEAEs by System Organ Class and Preferred Term

The following summary tables of TEAEs will be provided by SOC and PT using frequency counts and percentages (i.e., number and percentage of participants with an event):

- All unsolicited TEAEs
- All unsolicited TEAEs that are treatment-related
- All unsolicited TEAEs leading to withdrawal from study participation
- All unsolicited severe TEAEs
- All unsolicited severe TEAEs that are treatment-related
- All unsolicited treatment-emergent AESIs
- All unsolicited medically attended TEAEs
- All unsolicited medically attended TEAEs that are treatment-related

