6.4.2 Serious Adverse Events

An AE (including an AR) is considered an SAE if, in the view of either the Investigator or Sponsor, it results in any of the following outcomes:

- Death
- Life-threatening
- Inpatient hospitalization or prolongation of existing hospitalization
- Persistent or significant incapacity or substantial disruption of the ability to conduct normal life functions
- Congenital anomaly or birth defect
- Medically important event

The overall summary of unsolicited TEAEs in Section 6.4.1.1 will include the following:

- Any unsolicited serious TEAEs
- Any unsolicited serious treatment-related TEAEs

The following summary tables of unsolicited serious TEAEs within 28 days and overall period will be provided by SOC and PT using frequency counts and percentages (i.e., number and percentage of participants with an event):

- All unsolicited serious TEAEs
- All unsolicited serious TEAEs that are treatment-related

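### SAP tables of SAEs, treatment-related SAEs and MAAEs count unsolicited events only, so a serious or medically attended solicited reaction is left out of a primary safety endpoint

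*SAP*

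**What the plan says.** SAP 3.1 states the endpoint without restriction, over the whole follow-up to the Day 181 visit: "Frequency of any serious adverse events (SAEs), adverse events of special interest (AESIs), medically attended adverse events (MAAEs), and AEs leading to withdrawal". Protocol section 3 agrees.

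The analysis sections are narrower. SAP 6.4.1 plans to summarise "Unsolicited SAE, unsolicited AESI, unsolicited MAAE, and unsolicited AE leading to withdrawal from the study up to 28 days after vaccination and overall period". The overall table in SAP 6.4.1.1 has the row "Any unsolicited medically attended TEAEs", SAP 6.4.1.2 has "All unsolicited medically attended TEAEs that are treatment-related", and the SAE tables in SAP 6.4.2 include "All unsolicited serious TEAEs that are treatment-related". The listings of serious treatment-related and medically attended events in SAP 6.4.1.1 carry the same qualifier.

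Both documents accept that a solicited reaction can fall into these categories. SAP 6.4.2 opens with "An AE (including an AR) is considered an SAE if, in the view of either the Investigator or Sponsor". Among the solicited reactions that site staff must record in the solicited AR section of the eCRF, protocol 8.4.3 names "Solicited local or systemic AR that otherwise meets the definition of an SAE" and "Solicited local or systemic AR that results in a visit to a healthcare practitioner (HCP), to be recorded as an MAAE".

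SAP 6.4.3 treats every solicited reaction as causally related to vaccination. SAP section 1 gives the SAP precedence over the protocol, and SAP section 7 declares no change from the protocol's planned analyses.

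**The concern.** The endpoint asks how many participants had any SAE or MAAE. The tables answer how many had one that was unsolicited. The difference is the set of solicited reactions, starting on the day of injection or the six days after it, that were serious or took the participant to a healthcare provider.

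Because solicited reactions are all taken as related, a serious one is by definition a treatment-related SAE. It would be missing from the table meant to show such events, in the first human study of mRNA-1020 and mRNA-1030. A reader of that table would take a zero to mean that none occurred.

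**Working it through.** **Step 1. Follow two hypothetical events through the SAP.**

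| | Myalgia, onset Day 2, urgent-care visit | Fever, onset Day 2, overnight hospital admission |
|---|---|---|
| Meets the endpoint | Yes, MAAE | Yes, SAE |
| Unsolicited under SAP 6.4.1 | No: solicited term, onset inside the window | No, same reason |
| Overall table, SAP 6.4.1.1 | Not counted | Not counted |
| SOC/PT tables, SAP 6.4.1.2 and 6.4.2 | Not counted | Not counted, including as treatment-related |
| Solicited tables, SAP 6.4.3 | Counted by grade, day, onset and number of days | Same |
| Shown there as MAAE or SAE | No | No |

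**Step 2. Compare the SAP with protocol Table 9.**

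| Category | Table 9 limits to unsolicited? | SAP limits to unsolicited? | Result |
|---|---|---|---|
| SAE | No | Yes | Undeclared departure |
| Treatment-related SAE | No | Yes | Undeclared departure |
| MAAE | Yes | Yes | SAP follows Table 9; Table 9 and protocol 8.4.4 conflict with the endpoint and 8.4.3 |
| AESI | Yes | Yes | No practical effect: no concept in protocol Table 10 is a solicited term |
| AE leading to withdrawal | Yes | Yes | Recoverable: solicited AR is a withdrawal reason in protocol 7.3, and SAP 6.3.1 tabulates discontinuation by reason |

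**Step 3. Can the solicited grade tables stand in?** Protocol Table 7 has 4 local + 7 systemic = 11 terms.

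- For 7 of them (pain, axillary swelling, headache, fatigue, myalgia, arthralgia, chills), Grade 4 means an emergency room visit or an admission, without separating the two.
- For nausea/vomiting (1 term), Grade 4 has the added condition of hypotensive shock.
- Erythema, swelling/induration and fever (3 terms) are graded on other criteria. Check: 7 + 1 + 3 = 11.

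Grade 4 is therefore a partial proxy for SAEs, and it misses a reaction that is serious only as a medically important event. For MAAEs it is weaker still. An urgent-care or primary-care visit qualifies under protocol 8.4.4 and can follow a reaction of any grade. Two Grade 3 definitions, for nausea/vomiting and chills, already imply medical contact.

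**Step 4. Size.** The plan's only safety probability reproduces. With n = 70 per arm, 1 − (1 − p)^70 is 75.7% at p = 2% and 94.3% at p = 4%, against the stated 76% and 94%.

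One omitted participant with no other qualifying event is 1/70 = 1.43% of a planned arm, or 1/35 = 2.86% of an age group within an arm (protocol Table 4).

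The documents give no rate for serious or medically attended solicited reactions. The rates q below are assumptions, for participants whose only qualifying event is such a reaction:

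| Assumed q | Chance of at least one omission, arm of 70 | Chance across 7 × 70 = 490 mRNA recipients |
|---|---|---|
| 0.1% | 6.8% | 38.8% |
| 0.5% | 29.6% | 91.4% |
| 1% | 50.5% | 99.3% |

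Likewise, if the true incidence were 2% and half of the affected participants had only solicited events, the chance of seeing at least one in an arm's table would be 1 − 0.99^70 = 50.5%, not 75.7%.

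**The case against.** Five points can be made for the plan.

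- **The MAAE restriction comes from the protocol.** This is true. Table 9 limits that row to unsolicited events, and protocol 8.4.4 has investigators look for MAAEs among unsolicited AEs. The SAP is not at fault there, but the endpoint remains partly untabulated.
- **The protocol is ambiguous on SAEs.** A sentence in protocol 9.5.2, before Table 9, joins unsolicited AEs and SAEs with a slash and can be read as limiting both. But Table 9 applies the qualifier row by row and leaves it off both SAE rows, so the unrestricted reading is the better one.
- **A serious solicited reaction would not go unnoticed.** This is also true. The pause rules and 24-hour SAE reporting are unaffected, SAP 6.4 lists deaths without restriction, and the reaction stays in the graded tables. None of these yields an SAE or MAAE frequency by arm.
- **The solicited listings may cover these cases.** SAP 6.4.3 describes those listings as eDiary data, but that phrase may attach only to reactions persisting beyond 7 days, and the SAP promises a listing for all table data. I therefore do not claim that eCRF-recorded reactions go unlisted. A listing would still not replace the count.
- **Separate reporting of solicited and unsolicited events is a recognised convention, and the eCRF and table shells are not available.** Both are fair. The convention is acceptable if it is declared and the excluded events are shown somewhere. How a medically attended solicited reaction enters the analysis data cannot be checked from these documents.

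**Conclusion.** The concern holds. Followed as written, the SAP leaves a serious or medically attended solicited reaction with onset in the 7-day window out of the SAE, treatment-related SAE and MAAE frequencies, although the endpoint includes it. For the two SAE categories this is an undeclared departure from protocol Table 9. For MAAEs it carries through an inconsistency within the protocol. AESIs are unaffected, and withdrawals need only a cross-reference.

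The direction is certain, since the reported frequency can only be equal or lower. The size is unknown and may be zero; the per-arm and per-age-group percentages assume the planned group sizes and one omitted participant. The defect concerns final tabulation only. Safety monitoring during the study is unaffected, and so are the sample size and its stated probabilities.

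**What to change.** In SAP 6.4.1.1, 6.4.1.2 and 6.4.2, define the rows for any SAE, any treatment-related SAE, any MAAE and any treatment-related MAAE as unsolicited TEAEs plus solicited reactions that meet the criterion, for both the 28-day and overall periods. Use the Safety Set by vaccine received as the denominator, count each participant once, and keep an unsolicited-only sub-line. Build the matching listings the same way. Solicited reactions are already to be MedDRA-coded (SAP 6.4), so they can enter the SOC and PT tables. For withdrawals, add a row or a pointer to the disposition table.

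An acceptable alternative is to keep the restriction, declare it in SAP section 7, and add one by-arm table of solicited reactions that were serious, medically attended or led to withdrawal.

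The cost is SAP wording, table and listing programming, and a check that the Reactogenicity eCRF page carries seriousness and medical-attendance flags. The SAE rows need no protocol change, because the fix returns the SAP to Table 9. The MAAE row needs a note in SAP section 7 on the difference from Table 9, or alignment of Table 9 at the next amendment; protocol section 9 sets when an amendment is required.
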